5.1.2 ASSIGNED DOSAGE GROUPS

The first 5 patients in each dosage group will be assigned to receive the active medication in an open label fashion. These groups will be treated identically to the Randomized group with 4 exceptions:

- Patients in this group will have blood samples drawn at baseline before and 1h after dosing, and at each active treatment visit 1h after dosing to determine their blood levels of L1-79 for pharmacokinetic and pharmacodynamics analysis.
- Patients in this group will have EKG taken at baseline and within 3 days prior to the Week 1, 2, 3, and 4 treatment interval visits as well as at the 1 week and 4 week post dosing follow-up visits. Patients in this group will have vital signs, physical exam, and ASD assessments will be performed, including: ABC, SRS, RBS-R, CGI-S, and CGI-I be assessed at 1-week post-dosing. Patients in this group will have blood and urine samples drawn at baseline at baseline before dosing, at week 1, 2, and 3 active treatment visit 1h after dosing, and at the 1 week post dosing follow up for safety analysis.

Following the Week 1 visit for these patients and the completion of all assays for samples taken at the Week 1 visit, a report will be submitted to the FDA on the results from these patients. A second report on the results of these patients will be sent to the FDA following the final 1-week post-dosing visit for this group of patients.

5.1.3 RANDOMIZED GROUP

Following the enrollment of 5 open label patients as described in the Assigned Dosage Groups, an additional 15 patients at each dose level will be randomized 2:1 to receive either active drug or placebo (2 active to each placebo patient. These patients will be treated identically to those in the Assigned Dosage Groups with 3 exceptions:

1. No pharmacokinetic samples will be drawn,
2. No EKG will be performed
3. They will not have the 1 week follow-up, just the 1 month follow up.

After being randomized to a treatment arm each patient will be assigned a study number comprised of a 2-digit site identifier and a 3-digit patient identifier as described above.

Study numbers will not be assigned until a patient is qualified and entered into the trial. Screening failures will not be assigned numbers. However, a list of screen failures and their demographic data will be maintained by the Investigator.

Patients will be enrolled and receive their first dose within 3 weeks of completing the screening procedure.

5.1.4 PLACEBO ROLLOVER TO ACTIVE

- If the Investigator in collaboration with Yamo Pharmaceuticals (the manufacturer of the drug) believes that the L1-79 is sufficiently well tolerated and clinically useful to warrant continued treatment, then patients receiving placebo will be eligible for a 4 week course of treatment with L1-79 as outlined for the other patients treated with active drug in this protocol. At the present time, the permitted course of therapy does not extend past 4 weeks.
- The random code will only be broken after the last patient in a group has completed the last scheduled follow-up visit.
- Placebo treated patients who qualify for active treatment in a rollover fashion, and who desire to do so, will be indicated in the eCRF as having affirmatively requested active treatment under the protocol. They will then qualify for extended treatment with active medication under the existing protocol and new, active, medication will be assigned to them on an open label basis at the same dose as their group had been receiving.
- Placebo rollover patients will be seen at 3 scheduled visits plus a follow-up visit as described in [Appendix B](#).
 - There will be no Screening, as patients have already been screened
 - Rollover patients will not have any PK tests conducted
 - Baseline Visit
 - No randomization is required.
 - Roll over patients will get a physical (including vital signs)
 - Blood and urine samples will be taken for hematology, urinalysis and serum chemistry assessments.
 - No retained samples to be collected
 - All psychometric assessments described in [Appendix A](#) for the baseline visit will be taken
 - The initial 2 weeks of doses of active medication will be dispensed.
 - Week 2
 - A physical examination will be performed and the parents interviewed as to their observations regarding the effects of treatment over the past two weeks, and the final two weeks of active medication doses will be dispensed.
 - Patients will get a physical (including vital signs)

- No blood or urine samples will be taken
- No psychometric tests will be conducted at this visit.
- Week 4
 - The final active treatment assessment will be made, which will include a physical examination,
 - All blood and urine analysis described previously
 - No retained samples to be collected
 - All psychometric tests described for the 4 week visit in [Appendix A](#).
 - Patients will get a physical (including vital signs)
 - A week 4 ADOS will be taken
- 4 weeks post treatment follow-up
 - The final assessment will be made, which will include a physical examination,
 - All blood and urine analysis described previously
 - Patients will get a physical (including vital signs)
 - No retained samples to be collected
 - All psychometric tests described for the 4 week visit in [Appendix A](#).

5.1.5 EMERGENCY BREAKING OF THE RANDOM CODE

In the event a patient has an emergency that requires knowing which regimen he was receiving in this trial, that information can be obtained by calling [contact] or [contact]. This number is for the use of the Investigator or other treating physician whose knowledge of the randomization is critical to the treatment of the patient.

5.2 Drug Administration

5.2.1 THE L1-79 REGIMEN

Subjects will receive either 100 mg or 200 mg or matching placebo t.i.d. for a total of 28 days of dosing. The doses of L1-79 were determined based upon preliminary clinical research in subjects between 2½ and 24 years of age and doses between 90 and 200 mg t.i.d..

5.2.2 THE PLACEBO REGIMEN

The matching placebo regimen consists of inert ingredients matched in taste, weight and appearance to the active drug and administered orally t.i.d. for 28 days.

5.2.3 DOSING INSTRUCTIONS

The study medication will be dispensed in containers that contain sufficient study drug for two weeks of t.i.d. dosing, plus 2 additional doses to be used if needed (44 doses) at the Day 0 and Week 2 visits. In order to maintain the double-blind, each dose will be

comprised of 2 capsules as described below. Thus, each biweekly drug allotment will consist of 44 packages of 2 capsules each sufficient for 3 daily doses times 14 days plus 2 extra doses to be used in the event that a dose or two is lost. Subjects will be instructed to take a dose (2 capsules) in the morning upon arising, afternoon at approximately 4 pm, and just prior to bed time. Capsules can be taken orally, or their contents can be mixed with food or drink as deemed necessary by the caregiver to facilitate the administration of the medication. Care will be taken to assure that 8 oz of water are given at the time of dosing to maintain hydration. For subjects unable to swallow capsules the may take the drug in food or drink. Patients should also be cautioned about potential sedative effects and instructed not to conduct activities like driving, which require alertness.

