5.2.3.1 First Dose Safety Observation

The first dose of L1-79 in every patient will be administered at the study site, and each patient will be observed for a minimum of 2 hours post-dosing in order to assess adverse events. Special attention should be paid to potential AE known to be associated with impaired catecholaminergic function such as dystonias, cardiovascular events, extrapyramidal symptoms, and so forth.

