5.5.1.6 PK Assessment

- Blood samples will be taken at baseline both before and 1h after dosing, and at each of the 4 weekly active treatment visits 1h after dosing in the Assigned Dosage Group for the purpose of measuring serum levels of L1-79.

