5.5.1.8 Clinical Laboratory Safety Assessments

The following parameters will be measured for the Randomized Groups at screening, at week 4, and at the 4-week follow-up, and in addition for the Assigned Dosage Groups at each weekly visit and the 1 Week Follow up using the central laboratory provided:

- Urinalysis
 - Color
 - Clarity/turbidity
 - pH
 - Specific gravity
 - Glucose
 - Ketones
 - Nitrites
 - Bilirubin
 - Urobilirubin
 - Blood
 - Protein
 - RBC
 - WBC
 - Squamous epithelial cells
 - Casts
 - Crystals
 - Bacteria
 - Yeast
 - Fractionated urinary catecholamines
 - Vanillylmandelic acid
- Hematology
 - hemoglobin,
 - hematocrit,
 - platelet count,
 - RBC
 - WBC with differential
- Serum Chemistry
 - sodium,
 - potassium,
 - chloride,
 - BUN,
 - creatinine,
 - AST,
 - ALT,
 - GGT,
 - LDH,
 - CO₂/bicarbonate
 - total protein,
 - albumin,
 - calcium,

- phosphorous,
- alkaline phosphatase,
- total bilirubin (direct, indirect, total),
- cholesterol,
- triglyceride,
- amylase, lipase
- T₄ & TSH
- Fractionated Plasma Catecholamines
- Metanephhrines, plasma free & fractionated.

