7.4 Labeling of Test Articles

Each drug container will contain 2 weeks of study drug and two extra doses to be used in the event a dose or two is lost, and will be labeled as follows,

- Protocol number
- Storage requirements
- Investigational use statement "Experimental Clinical Use Only"

Each dose consisting of 2 capsules will be individually wrapped and provided within the larger container will be labeled as follows:

Envelope Labels

Protocol HT 02-121 Investigational Drug--Limited by Federal Law to investigational Use
 
Patient No. XX-YYY
 
Store at room temperature
 
Contents: 1 individual dose comprised of 2 capsules each
 
Take 1 dose of 2 capsules by mouth at upon arising, at 4:00 PM and at bed time. Take with 8 oz. of water.
 
Batch #: XXXX
 
Keep out of Reach of Children

Each individual dose will be labeled as follows:

Side of Box

Protocol HT 02-121 Investigational Drug--Limited by Federal Law to investigational Use
 
Store at room temperature
 
Take 1 package of 2 capsules by mouth at upon arising, 1 capsule at 4:00 PM and one capsule at bed time. Take with 8 oz. of water.
 
Keep out of Reach of Children

--

Top of Box

Patient No: XX-YYY
 
Study HT 02-121
 
Box 1 [or 2]
 
Keep out of Reach of Children

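### Week 1–4 PK samples are specified as 1 h post-dose, but the visible text neither aligns the take-home dose with the clinic draw nor has either time recorded

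*Combined protocol and SAP*

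**What the plan says.** **Sampling.** Section 5.5.1.6 asks for blood before and 1 h after dosing at baseline, and then "at each of the 4 weekly active treatment visits 1h after dosing in the Assigned Dosage Group". Section 5.1.2 agrees: "at each active treatment visit 1h after dosing to determine their blood levels of L1-79". It also ties the Assigned-group safety blood and urine samples to the dose, "at week 1, 2, and 3 active treatment visit 1h after dosing". Section 5.5.1.8 schedules the same laboratory panel "for the Assigned Dosage Groups at each weekly visit and the 1 Week Follow up" and gives no time from dose.

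**Dosing.** Section 5.2.3 sets three doses a day, "in the morning upon arising, afternoon at approximately 4 pm, and just prior to bed time". The envelope label in Section 7.4 reads "Take 1 dose of 2 capsules by mouth at upon arising, at 4:00 PM and at bed time". Neither mentions visit days. Section 7.2 has the pharmacist prepare drug to be taken home. The only dose placed at the clinic is in Section 5.2.3.1: "The first dose of L1-79 in every patient will be administered at the study site".

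**Use of the data.** Section 3.2.3 says the PK results will establish exposure at the two doses. Sections 4.3, 5.1.1 and 5.9.3.3 send the first-week safety and PK data from the 100 mg group to the FDA before anyone receives 200 mg.

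**The concern.** On Day 0 the dose is given on site, so a sample 1 h later is under the clinic's control. From Week 1 on, a caregiver who follows the label will usually have given the morning dose before leaving for the clinic. The next scheduled dose is in mid-afternoon. A draw at an ordinary daytime visit then falls at whatever interval the appointment happens to produce, yet the protocol describes it as a 1-h sample.

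With five patients per dose level, one concentration per weekly visit and descriptive analysis only (Section 6.1), there is little to average out a mistimed sample. If neither time is recorded, an off-time sample cannot be identified or corrected later. A difference between the Day 0 and Week 1 concentrations could then reflect repeated dosing or sampling delay, and nobody could tell which. The pharmacodynamic readings may be affected too, because the safety panel in Section 5.5.1.8 includes plasma catecholamines and metanephrines.

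**Working it through.** The plan states no figure to reproduce. The check sets the texts side by side and then counts the samples affected.

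**1. What each place says about Weeks 1–4 in the Assigned Dosage Groups**

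| Place | Content | Aligns dose and draw? |
|---|---|---|
| 5.1.2, 5.5.1.6 | PK blood 1 h after dosing at each weekly visit | States the target only |
| 5.1.2 | Safety samples 1 h after dosing, Weeks 1–3 | States the target only |
| 5.2.3; 7.4 envelope label | Doses on arising, about 4 pm, bedtime | No visit-day wording |
| 5.2.3.1 | First dose on site | Day 0 only |
| 5.9.2.3–5.9.2.6 (visit lists) | PK and safety draws; confirmation that medication was taken | No clinic dose, no time from dose, no window |
| 5.9.3.1 | Blood at each weekly visit | No time from dose |
| Appendix A footnote | Before and 1 h after the first dose | Baseline only |
| Appendix E | Tube handling and storage | No draw time requested |

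**2. When both texts are met**

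The elapsed time is draw time minus time of last dose, and the target is 1 h. Given the scheduled doses, the target is met if the draw is 1 h after waking, or at about 4 pm + 1 h = 5 pm. A draw 1 h after the bedtime dose is not a practical clinic visit. No visible passage schedules visits at these times.

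To illustrate, assume a dose on arising at 06:00–08:00 and a draw at 09:00–15:00. Neither range is in the documents.

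- Shortest interval: 09:00 − 08:00 = 1 h
- Longest interval: 15:00 − 06:00 = 9 h

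The target is reached only at the edge of that range. A visit timed to the 4 pm dose lies outside the illustration and could meet it.

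**3. Samples affected**

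- PK samples per patient: 2 at baseline + 4 weekly = 6, of which 4 have no stated means of achieving the 1-h timing.
- Per dose level (5 patients): 5 × 6 = 30, of which 5 × 4 = 20.
- Both levels: 2 × 30 = 60, of which 2 × 20 = 40.
- First-week data at 100 mg: 5 × 1 = 5 Week 1 samples.
- Safety sets tied to 1 h: 3 per patient (Weeks 1–3), 5 × 3 = 15 per dose level, 2 × 15 = 30 in all.

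**4. Size of the error in concentration**

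This cannot be computed. It needs at least a half-life and a time to peak, and the documents give neither.

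**The case against.** The strongest reply is that the texts do not contradict each other. Three doses are scheduled, one at about 4 pm, and no visit has a clock time. An afternoon visit with a draw at about 5 pm, or an early draw within an hour of waking, satisfies everything without any extra dose. Section 5.1.2 also lists its sampling rule among the ways in which these patients differ from the randomized group, so it can be read as a specific rule beside the general instruction. This stands. A reader might infer that the instructions are impossible to follow together, or that a 1-h sample would need a fourth dose that day. The documents support neither: the sections are unaligned, and no passage orders an added dose.

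Appendix A has a Study Drug Administration form at Weeks 1–4, which might capture dose times or imply clinic dosing. It does not establish either. As extracted, the row is unmarked at baseline, where the on-site dose occurs, and the same form appears in Appendix B for rollover patients, who have no PK. Still, its fields are not visible. Nor are the body of the consent form (Appendix C) or the Study Compliance Agreement (Appendix D), so visit-day wording there cannot be excluded. That home dosing is meant is inferred from Sections 7.2 and 5.2.3.1; the label does not say so.

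A reader might also infer that the timing error could exceed the two-fold difference between the doses. That takes two assumptions from outside the documents: that 1 h is already past the peak, and that the half-life is short. With fraction = 0.5^(delay/half-life), delays of 1, 2 and 3 h give 0.71, 0.50 and 0.35 at an assumed half-life of 2 h, and 0.92, 0.84 and 0.77 at 8 h. Only one of the six values is below one half. If 1 h comes before the peak, a later draw could read higher and the direction would reverse.

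Finally, both dose levels follow the same instructions, so delay may mainly add scatter to the 100 versus 200 mg comparison. That comparison cannot influence escalation, because only 100 mg data exist then. Section 5.1.1 states the condition for escalation in terms of safety data, and the plan prespecifies no Day 0 versus Week 1 test. These points limit the consequence. They do not supply the missing alignment or the missing times.

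**Conclusion.** The concern holds as a gap between sections. For the Assigned Dosage Groups the protocol specifies 1-h samples at Weeks 1–4, and the visible text neither says how the visit-day dose and the clinic draw are brought together nor requires either time to be recorded. Four of six PK samples per patient may be taken at unverified intervals: 20 of 30 per dose level and 40 of 60 overall. These include the Week 1 samples in the FDA escalation report. The 1-h rule for safety samples is affected at Weeks 1–3 only; no dose-relative time is given for Week 4.

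The conclusion rests on the visible dosing instructions, labels, visit lists and schedule, and on the reading that doses after the first are normally taken away from the clinic. It does not depend on any half-life. The counts are samples at risk; how many would actually be off-time is not known.

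**What to change.** 1. Reconcile Section 5.2.3 and the envelope label with Sections 5.1.2, 5.5.1.6, 5.9.2.3–5.9.2.6 and Appendix A for the Week 1–4 visits. How visit-day dosing is arranged is a clinical decision for the sponsor and the investigator, and no rule is proposed here. Bring Section 5.5.1.8 into line on the timing of the safety samples.
2. Record in the eCRF the clock time of the last dose before each draw and the clock time of the draw.
3. Report each concentration against actual elapsed time, and flag samples outside a tolerance around 1 h that is stated in advance. Show these times in the report sent to the FDA.

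The cost is some rewording and two time fields for 10 patients. Some samples may be flagged as off-time. The times need to be captured at the visit, because they cannot be reliably recovered afterwards.

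While the labels are open, note a separate inconsistency in Section 7.4. The side-of-box text, "Take 1 package of 2 capsules by mouth at upon arising, 1 capsule at 4:00 PM and one capsule at bed time", gives different capsule counts from the envelope label for the later two doses, and the two must also be reconciled.

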5.2.3.1 First Dose Safety Observation

The first dose of L1-79 in every patient will be administered at the study site, and each patient will be observed for a minimum of 2 hours post-dosing in order to assess adverse events. Special attention should be paid to potential AE known to be associated with impaired catecholaminergic function such as dystonias, cardiovascular events, extrapyramidal symptoms, and so forth.

5.3 Potential Side Effects and Treatment

The levo form of L1-79 (L-AMPT) is marketed under the name of Demser for the presurgical treatment of pheochromocytoma. Demser is prescribed for adults and children over 12 at doses between 1-4 g/d, with the lowest label dose of Demser being 250 mg qid. This is higher than the highest dosage used in this study. L1-79 is a racemate it contains the dextro form of the amino acid isomer and only 50% of the active Demser ingredient as determined by measuring the optical rotation. L1-79 has been tested in rodents and dogs and found to be well tolerated at multiples of the dose to be used in this trial. Based upon 4 week toxicological reports in rats and dogs a sufficient toxicology profile has been elaborated to support the use of L1-79 in a 4-week study in humans.

At the approved doses of ≥ 2 g/d Demser may be associated with crystalluria, sedation, and other effects reported to have been mild. Mild depression and difficulties in sleeping have also been reported at these higher doses. These effects were observed to be transient. Investigators should instruct subjects and caregivers to maintain patient hydration, and to be aware of potential sedative effects that would limit the use of the drug when using power equipment or driving. It should be noted that the highest dose in this trial is equivalent to 300 mg of Demser daily, or 15% of the 2 g/d dose.

5.4 Concomitant Medication

Patients are permitted only 1 concomitant medication in this trial. Patients should be assessed for concomitant medications during the screening process and weaned down to the lowest possible effective level for the duration of this trial, including all follow-up visits.

5.5 Clinical and Laboratory Procedures

Prior to starting any procedure associated with this study, the patient or caregiver must give written informed consent ([Appendix C](#)) to participate and agree to abide by the requirements of this study. Study personnel experienced with ASD patients and their families will take great care to explain in detail and in easy to understand terms the purpose, objectives, methods, tests, study schedule, and any other pertinent information that might influence the granting of consent to participate. Similarly, study staff will take great care to elicit and answer all questions that arise in the course of describing this trial and will answer all questions fully. A copy of the consent form will be maintained with the patient's records.

This study will use the local certified clinical laboratory associated with the Investigators practice. CLIA certification and normal values will be obtained by the Investigator and provided to the Sponsor for each clinical lab used, and normal values will be updated after each calibration cycle.

A schedule of events can be found in [Appendix A](#).

5.5.1 SCREENING EVALUATION FOR INCLUSION/EXCLUSION CRITERIA

Criteria for inclusion and exclusion of potential study subjects are outlined in Sections [4.1](#) and [4.2](#). All potential study subjects must be evaluated for the presence of all inclusion criteria and the absence of all exclusion criteria before enrollment in this study.

5.5.1.1 Medical History

Background information will be recorded once for each patient during screening for this study. This information includes age, gender, race and medical history including concomitant diseases and conditions associated with organ systems and chronic infectious diseases, as well as a detailed family history to ascertain any heritability of autism, cognitive dysfunction, epileptic or other diseases associated with autism.

Caregivers will be questioned about the patient's prenatal history, possible exposure to pesticides or other toxins, pre-natal maternal inflammation, fetal alcohol syndrome, and drugs taken by the mother during prior to, during, and after pregnancy.

In addition to the usual medical history questions asked of patients with ASD, patients and caregivers will be queried about their use of alcohol sugars such as xylitol, mannitol, and the dental health of the study subjects.

